## PROTOCOL SYNOPSIS

Study Title	A 24 Week, Open-Label Study to Evaluate the Efficacy and Safety of Upadacitinib in Patients with Moderate-to-Severe Prurigo Nodularis
Sponsors	[name]
Study Objectives	
Primary Objective: To explore the effectiveness of upadacitinib in patients with prurigo nodularis.
 
Secondary Objectives: To explore the safety of upadacitinib in patients with prurigo nodularis.

Study Design	A single center, open-label study of 25 subjects to assess 24 weeks upadacitinib in patients with moderate-to-severe prurigo nodularis.
Study Centers	Eczema Treatment Center of New Jersey [name]
Study Population	25 adult male and female subjects with moderate-to-severe prurigo nodularis
Main Inclusion Criteria	
 
1. Male or female adult 18-64 years of age at time of screening.
 
2. Diagnosis of prurigo nodularis for <math>\geq</math> 3 months.
 
3. Moderate-to-Severe prurigo nodularis as determined by at least 10 PN lesions on legs and/or arms and/or trunk at screening and baseline .
 
4. Failure of at least a 2-week course of medium to super potent TCS or TCS is not medically advisable for subject.
 
5. Females of childbearing potential must not have a positive serum pregnancy test at the Screening Visit and must have a negative urine pregnancy test at the Baseline Visit prior to study drug dosing. Note: subjects with borderline pregnancy test at Screening must have a serum pregnancy test <math>\geq</math> 3 days later to determine eligibility. If female, subject must be postmenopausal OR permanently surgically sterile OR for females of childbearing potential practicing at least one protocol specified method of birth control, that is effective from the Baseline Visit through at least 30 days after the last dose of study drug. Female subject must not be pregnant, breastfeeding or considering becoming pregnant during the study or for approximately 30 days after the last dose of the study drug.
 
6. Subject is a candidate for systemic therapy per investigator discretion.
 
7. Able and willing to give written informed consent prior to performance of any study-related procedures.
 
8. Subject must be in general good health as judged by the Investigator, based on medical history, physical examination.
 

Main Exclusion Criteria	
 
1. Presence of skin condition other than prurigo nodularis or atopic dermatitis that may interfere with study assessments.
 
2. Diagnosis of active atopic dermatitis at screening and baseline.
 
3. PN secondary to medications.
 
4. PN secondary to medical conditions such as neuropathy or psychiatric disease.
 
5. Severe concomitant illness(es) under poor control that, in the investigator's judgment, would adversely affect the patient's participation in the study.
 
6. Severe renal conditions (eg, patients with uremia and/or on dialysis)
 
7. Participants with uncontrolled thyroid disease.
 
8. Active tuberculosis or non-tuberculous mycobacterial infection, or a history of incompletely treated tuberculosis unless documented adequately treated. Patients with latent TB at screening may be enrolled if tuberculosis treatment is initiated prior to first dose.
 
9. Diagnosed active endoparasitic infections; suspected or high risk of endoparasitic infection, unless clinical and (if necessary) laboratory assessment have ruled out active infection before randomization.
 
10. Active chronic or acute infection (except HIV infection) requiring treatment with systemic antibiotics, antivirals, antiprotozoals, or antifungals within 2 weeks before the screening visit or during the screening period.
 
11. Known or suspected immunodeficiency.
 
12. Active malignancy or history of malignancy within 5 years before the baseline visit, except completely treated in situ carcinoma of the cervix, completely treated and resolved non-metastatic squamous or basal cell carcinoma of the skin.
 

Study Endpoints	Primary Endpoint: Proportion of participants with improvement (reduction) in worst-itch numeric rating scale (WI-NRS) by $\geq 4$ from baseline to Week 12. [Time Frame: Baseline to Week 12 ]WI-NRS is a patient-reported outcome (PRO) comprised of a single item rated on a scale from 0 ("No itch") to 10 ("Worst imaginable itch). Secondary Endpoints: Proportion of patients with improvement in worst-itch numeric rating scale (WI-NRS) by $\geq 4$ from baseline to Week 24 IGA PN-S 0 or 1 at weeks 12 & 24 IGA PN-A 0 or 1 at week 12 & 24 Percent improvement of PN-S & PN-A at week 12 & 24 DLQI improvement at weeks 12 & 24 Adverse Events
References	Tessa B. Mullins, Poonam Sharma, Christopher A. Riley, Sidharth Sonthalia. Prurigo Nodularis. StatPearls [Internet]. Treasure Island (FL): StatPearls Publishing; 2021 Jan. 2020 Sep 15.  Eric H Kowalski, Diana Kneiber, Manuel Valdebran, Umangi Patel, Kyle T Amber. Treatment-resistant prurigo nodularis: challenges and solutions. Clin Cosmet Investig Dermatol. 2019 Feb 28;12:163-172. doi: 10.2147/CCID.S188070. eCollection 2019.

## 2 ETHICS AND REGULATORY OBLIGATIONS

### 2.1 Institutional Review Board (IRB)

Written IRB approval of this protocol must be obtained before the study is initiated. Compliance with Title 21 of the US Code of Federal Regulations (CFR), Part 56, is required in order to protect the rights and welfare of human subjects involved in this study.

### 2.2 Ethical Conduct of the Study

The study will be conducted in accordance with the ethical principles that have their origins in the Declaration of Helsinki and its amendments. In addition, the study will be performed in compliance with Good Clinical Practices (GCP), including the archiving of essential documents.

## **2.3 Subject Information and Consent**

The Informed Consent Form will be reviewed and approved by the IRB. The purpose, duration and possible risks and benefits will be explained to each potential subject. Consent in writing must be obtained from the subject before enrollment into the study. Consents will be signed and dated as required by Title 21 of CFR, Part 50. The consent will also comply with the requirements of the Health Insurance Portability and Accountability Act (HIPAA). The original, signed Informed Consent Form will be retained by the Investigator. A signed copy of the Informed Consent Form will be given to the subject. Each subject will be assigned a subject number that will be used in lieu of the subject's name on further research documentation.

## **3 INTRODUCTION**

### **3.1 Overview of Prurigo Nodularis and Study Rationale**

Prurigo Nodularis (PN) is a chronic skin disorder that presents as multiple firm nodules commonly located on the extensor surfaces of the extremities. The lesions are very pruritic and commonly associated with another disorder of cutaneous hypersensitivity such as atopic dermatitis. Treatment for PN varies from topical and intralesional corticosteroids for mild cases to phototherapy and systemic immunosuppressives for more severe cases. Upadacitinib is a novel selective orally available JAK1 inhibitor with the potential to decrease T helper 2 cell-mediated skin inflammation and itch mediated by JAK1, while having minimal inhibitory effects on JAK2 and JAK3. This study will evaluate the safety and efficacy of upadacitinib in prurigo nodularis itch improvement as well as improvement of PN lesions.

## **4. STUDY OBJECTIVE**

To explore the effectiveness and safety of upadacitinib in patients with moderate-to-severe prurigo nodularis.

## **5. INVESTIGATIONAL PLAN**

### **5.1 Overall Study Design and Plan**

25 subjects with prurigo nodularis with at least 10 PN lesions on arms, legs and/or trunk with moderate-to-severe itch will receive upadacitinib 15mg once daily.

### **5.2 Study Population Criteria**

Males and females 18-64 years of age with moderate-to-severe prurigo nodularis

### **5.2.1 Inclusion Criteria**

Patients who meet all of the following criteria will be enrolled in the study:

1. Male or female adult 18- 64 years of age at time of screening.
2. Diagnosis of prurigo nodularis for  $\geq$  3 months
3. Moderate-to-Severe prurigo nodularis as determined by at least 10 PN lesions on legs and/or arms and/or trunk at screening and baseline.
4. Failure of at least a 2 week course of medium to super potent TCS or TCS is not medically advisable for subject.
5. Females of childbearing potential must not have a positive serum pregnancy test at the Screening Visit and must have a negative urine pregnancy test at the Baseline Visit prior to study drug dosing. Note: subjects with borderline pregnancy test at Screening must have a serum pregnancy test  $\geq$  3 days later to determine eligibility. If female, subject must be postmenopausal OR permanently surgically sterile OR for females of childbearing potential practicing at least one protocol specified method of birth control, that is effective from the Baseline Visit through at least 30 days after the last dose of study drug. Female subject must not be pregnant, breastfeeding or considering becoming pregnant during the study or for approximately 30 days after the last dose of the study drug.
6. Subject is a candidate for systemic therapy
7. Able and willing to give written informed consent prior to performance of any study-related procedures.
8. Subject must be in general good health as judged by the Investigator, based on medical history, physical examination.

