#### **5.6.7.1 Worst-Itch Numerical Rating Scale**

(WI-NRS) is a PRO comprised of a single item rated on a scale from 0 ("No itch") to 10 ("Worst imaginable itch"). Participants are asked to rate the intensity of their worst pruritus (itch) over the past 24 hours using this scale. 0.1 Worst Itch Numeric Rating Scale. [See Appendix B](#)

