### **8.2.1 Additional Statistical Considerations**

The objective of the statistical analyses is to assess the efficacy and safety of upadacitinib for the treatment of subjects with moderate to severe PN who are candidates for systemic therapy. The Primary Analysis for all efficacy endpoints will be conducted after all continuing subjects have completed the study activities up to Week 16. The Intent-to-Treat (ITT) Population consists of all randomized subjects and will be used for the efficacy analyses. A Per-Protocol Population may be defined if deemed necessary to exclude subjects with major protocol violations. The criteria to define the Per-protocol Population will be detailed in the SAP. Subjects to be excluded from the Per-Protocol Population will be finalized before week 16. The Per-Protocol Population, if defined, will be used to analyze the primary efficacy endpoint.

The Safety Population consists of all randomized subjects who received at least 1 dose of study drug. An All Upadacitinib Treated Population consists of all subjects who received at least one dose of upadacitinib in the study. This population will be used to provide a comprehensive summary of safety.

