#### **Statistical Analyses for Efficacy**

All efficacy endpoints will be analyzed on the ITT population. In addition, the primary efficacy endpoints will be analyzed in the Per-Protocol Population, if defined.

No missing data imputation will be applied, and all assessments prior to premature discontinuation from study drug will be used.

Statistical Analyses for Safety – how will data be summarized? % of patients with AEs? The safety analyses will be carried out using the Safety Population. % of patients with AE's will be assessed inclusive of physical examination, laboratory assessments, and vital sign abnormalities.

Note that missing safety data will not be imputed.

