### **8.3 Schedule of Events**

	V1	V2	V3	V4	V5	V6	V7	V8
Procedures/Non-Procedure Description	SCR	BL	WK4	WK8	WK12	WK16	WK20	WK24
Informed Consent	X							
Medical History and Demographics	X	X						
Inclusion/Exclusion Criteria	X	X						
Prior/Concurrent Medications/Procedures	X	X	X	X	X	X	X	X
Physical Examination	X	X	X	X	X	X	X	X
Serum Pregnancy	X							
Hepatitis B & C profile. Quantiferon Gold	X							
Safety Labs	X					X		X
Urine Pregnancy Test		X	X	X	X	X	X	X
Safety / AE Assessment	X	X	X	X	X	X	X	X
Patient Reported Outcomes / Questionnaires		X	X	X	X	X	X	X
Clinical Severity / Efficacy Assessments	X	X	X	X	X	X	X	X
Pharmacy Dispense/Drug Accountability			X	X	X	X	X	X

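### Section 5.1's moderate-to-severe itch is not carried into the enrolment criteria, so a subject whose baseline itch is too low to meet the primary endpoint can be enrolled; MINOR, a cheap improvement

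*Combined protocol and SAP*

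**What the plan says.** Section 5.1 describes the subjects who will be treated as those "with at least 10 PN lesions on arms, legs and/or trunk with moderate-to-severe itch". It gives no scale, cut-off or visit for the itch.

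Section 5.2.1, item 3, is the severity criterion that decides enrolment: "Moderate-to-Severe prurigo nodularis as determined by at least 10 PN lesions on legs and/or arms and/or trunk at screening and baseline". The synopsis has the same criterion: "Moderate-to-Severe prurigo nodularis as determined by at least 10 PN lesions on legs and/or arms and/or trunk". No other inclusion or exclusion item, in the synopsis or in Sections 5.2.1 and 5.2.2, sets a WI-NRS or IGA value.

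The primary endpoint is the proportion of subjects whose WI-NRS falls by at least 4 points on a 0 to 10 scale. The scale is a single 24-hour recall item: "Participants are asked to rate the intensity of their worst pruritus (itch) over the past 24 hours using this scale". A secondary endpoint is IGA PN-A of 0 or 1 at Weeks 12 and 24, with no change from baseline required.

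On the analysis set, Section 8.2.1 states: "The Intent-to-Treat (ITT) Population consists of all randomized subjects and will be used for the efficacy analyses". The efficacy subsection adds: "All efficacy endpoints will be analyzed on the ITT population". On missing values: "No missing data imputation will be applied, and all assessments prior to premature discontinuation from study drug will be used". The Schedule of Events (Section 8.3) starts the row "Patient Reported Outcomes / Questionnaires" at Visit 2, the visit at which eligibility is rechecked.

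**The concern.** The population described in Section 5.1 and the population that can be enrolled under Section 5.2.1 are not the same. The difference lies in the variable on which the primary endpoint is built.

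In a single-arm exploratory study the observed proportion is the result; there is no control arm to absorb a feature of the enrolled sample. A subject who starts too low on the itch scale lowers the primary rate whatever the drug does. A subject who starts and stays at PN-A 0 or 1 raises the PN-A rate whatever the drug does. Baseline WI-NRS and IGA are both collected, but the plan specifies no baseline summary and no analysis that would show either effect.

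**Working it through.** **No planned figure to reproduce.** The sample size of 25 (Section 8.2) is given without a target rate, power or precision. What follows is scale arithmetic and an illustration.

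**Step 1: which itch baselines cannot respond.** A fall of at least 4 to a floor of 0 needs a baseline of at least 4. Baselines 0, 1, 2 and 3, which are 4 of the 11 scale values, cannot meet the endpoint. No listed criterion excludes them. The result is the same whether the primary time point is Week 12 or Week 16, both of which appear in Section 8.2.

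**Step 2: which subjects start at the PN-A target.** Appendix A grades PN-A by the share of nodules with excoriations or crusts, and a score of 1 allows up to about 10%. With 10 nodules, at most 0.10 × 10 = 1 may be excoriated; with 20 nodules, at most 2. Such subjects meet the lesion count and are already at PN-A 0 or 1. PN-S is different: a score of 1 allows at most about 5 nodules, so 10 or more normally means PN-S of 2 or higher.

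**Step 3: effect on the reported proportions.** Let n = 25, all assessed, and let k be the assumed number of such subjects. The definition of ITT refers to randomised subjects; since nobody is randomised, I read it as all enrolled subjects. The rates of 60% and 50% are also assumptions.

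| | Formula | k = 1 | k = 3 |
|---|---|---|---|
| Highest attainable itch response | (25 − k)/25 | 96% | 88% |
| Reported itch response, 60% in the others | 0.60 × (25 − k)/25 | 57.6% | 52.8% |
| Reported PN-A 0/1, 50% in the others | (k + 0.50 × (25 − k))/25 | 52% | 56% |

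The itch rate moves down by 2.4 or 7.2 points. The PN-A rate moves up by 2 or 6 points.

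**Step 4: compare with sampling error.** The 95% half-width at 60% is 1.96 × √(0.60 × 0.40/25) = 19.2 points. Every shift in Step 3 is well inside that.

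**Step 5: side effects of an itch minimum.** I simulated 4 million subjects per setting with stable true itch, no drug effect, and readings rounded and limited to 0 to 10. Assumed mean and between-subject SD were (7, 2), (6, 2) and (7, 1.5), each with a within-subject SD of 1, 1.5 or 2.

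- *Regression to the mean.* Requiring at least 4 on the baseline reading itself, rather than on a separate reading, raised the chance of a fall of 4 or more by between 0.02 points (0.65% against 0.63%) and 2.3 points (11.59% against 9.29%).
- *A separate reading used alone.* Among subjects with at least 4 on a separate reading, 1.8% to 13.4% still had a baseline below 4. Of 25 subjects that is 0.018 × 25 = 0.5 to 0.134 × 25 = 3.3, about the size of the problem being fixed.
- *Fewer subjects.* The half-width at 60% is 19.6 points with 24 subjects and 20.5 with 22.

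**The case against.** The strongest reply on itch is that Section 5.1 already asks for it, so treating a subject with a WI-NRS of 0 to 3 would contradict the protocol. In addition, PN is described as very pruritic. Subjects must have failed topical corticosteroids or be unsuited to them, must be candidates for systemic therapy, and must have stopped topical treatment before baseline. All this makes low itch less likely, and it rules out the stronger reading that the plan has no itch requirement at all. It does not close the gap. Section 5.1 is not a listed criterion and gives no number, the steroid requirement has an alternative route, and the synopsis leaves candidacy for systemic therapy to the investigator.

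On PN-A the reply is stronger. No passage promises a baseline PN-A level, so nothing is contradicted, and an absolute target without an entry minimum is a design choice. A reader might infer a second inconsistency here; the documents do not support that.

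The optional Per-Protocol Population might also be cited. It is aimed at major protocol violations, and a low-itch subject who meets every listed criterion is not one.

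Finally, the study is exploratory, with no target rate or hypothesis test. That stands, and it limits the severity.

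**Conclusion.** The mismatch between Section 5.1 and the enrolment criteria is real, and its effect on the primary proportion has a known direction: downward. The PN-A point is secondary and runs upward. Severity is MINOR.

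The size rests on assumption. The documents give no baseline distribution, and the number of affected subjects may be zero. With an assumed 1 or 3 of 25, the shifts run from 2 to 7.2 points, against a half-width of about 19. A reader might infer that the trial's results will be materially biased; the documents do not show that. What they show is that following the listed criteria permits the problem and that no planned table would reveal it.

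**What to change.** **Eligibility.** Reconcile Section 5.1 with Section 5.2.1 and the synopsis by adding a WI-NRS minimum, chosen and justified by the sponsor, to the inclusion criteria. A value of 4 is only the arithmetic minimum at which the endpoint is attainable; it is not a definition of moderate itch. Check it on the Visit 2 baseline reading before the first dose. A Visit 1 reading should not replace that check, for the reason shown in Step 5, and it would add a questionnaire that the schedule does not have at screening.

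**Analysis, whether or not enrolment has begun.** Keep the ITT analyses primary. Tabulate baseline WI-NRS, PN-A and PN-S. Pre-specify two supportive analyses: itch response in subjects with baseline WI-NRS of at least 4, and PN-A 0/1 in subjects with baseline PN-A of at least 2.

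**Cost.** One eligibility line, one table and two supportive analyses, all on data already collected. There are two downsides. Slightly fewer subjects are eligible or evaluable, with the loss of precision shown in Step 5. Selecting on the baseline reading also brings some regression to the mean: about 0 to 2.3 points for itch under the assumed distributions. The PN-A subset is selected on baseline in the same way, and its effect has not been quantified.

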### **5.2.2 Exclusion Criteria**

Patients will NOT be enrolled in this study if they meet any of the following criteria:

1. Presence of skin condition other than prurigo nodularis or atopic dermatitis that may interfere with study assessments.
2. Diagnosis of active atopic dermatitis at screening and baseline.
3. PN secondary to medications.

4. PN secondary to medical conditions such as neuropathy or psychiatric disease.
5. Severe concomitant illness(es) under poor control that, in the investigator's judgment, would adversely affect the patient's participation in the study
6. Severe renal conditions (eg, patients with uremia and/or on dialysis)
7. Participants with uncontrolled thyroid disease.
8. Active tuberculosis or non-tuberculous mycobacterial infection, or a history of incompletely treated tuberculosis unless documented adequately treated. Patients with latent TB at screening may be enrolled if tuberculosis treatment is initiated prior to first dose.
9. Diagnosed active endoparasitic infections; suspected or high risk of endoparasitic infection, unless clinical and (if necessary) laboratory assessment have ruled out active infection before randomization.
10. Active chronic or acute infection (except HIV infection) requiring treatment with systemic antibiotics, antivirals, antiprotozoals, or antifungals within 2 weeks before the screening visit or during the screening period.
11. Known or suspected immunodeficiency.
12. Active malignancy or history of malignancy within 5 years before the baseline visit, except completely treated in situ carcinoma of the cervix, completely treated and resolved non-metastatic squamous or basal cell carcinoma of the skin.
13. Use of oral systemic medications or phototherapy for the treatment of prurigo nodularis within 4 weeks.
14. Patient received UVB phototherapy within 2 weeks of Baseline.
15. Patient used topical therapies within 1 week of the Baseline Visit.
16. Patient has used dupilumab within 12 weeks of Baseline Visit.

- 17.. Patient has a known hypersensitivity to the excipients of upadacitinib.
- 18.Presence of significant lab abnormality or uncontrolled medical condition that in the opinion of the investigator would affect patient safety during the trial.
19. . Prior use of upadacitinib.

### **5.3 Source of Subjects and Recruitment Methods**

The Investigator will manage the recruitment of subjects upon approval of the study by the Institutional Review Board. Subjects may be recruited from internal patient lists from the investigator's clinic and external IRB approved advertisements. The study site will manage recruitment campaigns with IRB approved documents.

### **5.4 Subject Enrollment and Treatment Assignment**

25 adult subjects of either gender with moderate-to-severe prurigo nodularis will receive upadacitinib 15mg once daily. Dosage will be increased to 30mg QD at week 8 based on subject response. See dosage adjustments below. IP will be managed by site personnel and stored in a temperature controlled limited access area at the study site. Accountability records will be maintained by site personnel for all IP receipt, dispensation and returns.

